#### 4.3 Case exclusion criteria:

- Signed the informed consent, entered the study but was found not to meet the inclusion criteria during the project supervision or after the completion of the study;
- Did not sign the informed consent;
- The intervention was not performed according to the treatment standards and had poor compliance;
- Failed to accept the intervention, did not comply with or assume the corresponding responsibilities and obligations of the informed agreement.

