Eligible patients were screened before surgery, and an informed consent form was signed. Patients enrolled in the experiment were randomly assigned into one of the three groups. They are early feeding group (EOF 1, EOF 2) and late feeding group (control group). Late feeding group (Group C): Group C patients observed 30min vital signs, returned to the ward to fast and drink for at least 6 h, and gradually drink and eat after anal exhaust. Early drinking water group (EOF 1): EOF 1 group received water in the resuscitation room; early drinking carbohydrate group (EOF 2): EOF 2 group received 200ml 12.5% carbohydrate (100ml containing 12.5g maltodextrin, fructose and glucose) in the resuscitation room.

To evaluate the resuscitation room of patients in the early feeding group: Steward awake score of 6 and awake level 3,5ml / kg lean weight 12.5% carbohydrate or water according to the need of consent. The process of drinking carbohydrates or water is to take 30ml orally first. After observing no abnormal swallowing, the patient was instructed to drink the remaining drinks as needed. After the patient returned to the ward, the liquid diet began to gradually excessive into the normal diet. When the patient was able to tolerate a normal diet, the intravenous fluids were stopped.

Evaluation process of drinking index:

1 ) Steward Score: awake: 0-no response to stimulus; 1-some response to stimulus; 2-full awake.(2) Respiratory tract patency: 0-patient's respiratory tract needs support; 1-patient's respiratory tract can maintain patency without support; 2-patient can cough according to the doctor's guidance.(3) Body mobility: 1 point-the patient has no body activity; 2 points-the unconscious activity of the patient's limb; 3 points-the patient's limb can carry out the conscious activities;

2 ) Grade of sobriety: according to the awake degree of the patient's consciousness: Grade 0: the patient is completely in the sleep state, No response when calling; Level Protocol version: May 17, 2023

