1: The patient is falling asleep, However, head and neck movement, eye opening, or limb movement occurs during breathing; Grade 2: the patient is awake, Have the same performance as level 1, At the same time can also open the mouth, stretch the tongue; Grade 3: the patient is in an awake state, Have the same performance as the level 2, At the same time, they can also clearly tell their own name, age and other information; Grade 4: The patient is awake, Have the same performance as level 3, It can also accurately identify the surrounding environment, And tell you clearly where you are.3.

3 ) The early feeding group (EOF 1 and EOF2 group) did not need to wait for peristalsis. According to the wishes of the patients, the dose was completed within 2 hours after the operation

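### Section 4.3 excludes patients already entered for poor compliance or for not accepting the intervention, while the drinking arms and group C have different things to comply with, so the comparison with group C is open to bias of unknown size and direction

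*Protocol*

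**What the plan says.** Section 4.3 of the protocol is a list of case exclusions, separate from the eligibility exclusions and the dropout standard in 4.2. Its first bullet, which begins "Signed the informed consent, entered the study but was found not to meet the inclusion criteria during the project supervision or after the completion of", shows that it reaches people already in the trial. Two further bullets concern adherence. Bullet 3 reads "The intervention was not performed according to the treatment standards and had poor compliance". Bullet 4 reads "Failed to accept the intervention, did not comply with or assume the corresponding responsibilities and obligations of the informed agreement".

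Section 3.1.2 sets out what each arm has to do.

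- **Group C** is "returned to the ward to fast and drink for at least 6 h, and gradually drink and eat after anal exhaust".
- **EOF 1 and EOF 2** start with a recovery check: "To evaluate the resuscitation room of patients in the early feeding group: Steward awake score of 6", together with an awake level of 3. A first 30 ml is then swallowed, and "After observing no abnormal swallowing, the patient was instructed to drink the remaining drinks as needed".
- **Amount and timing of the drink.** One sentence says that the "EOF 2 group received 200ml 12.5% carbohydrate". A later one gives both drinking arms a volume of 5 ml per kg lean weight. The last item of the section says "According to the wishes of the patients, the dose was completed within 2 hours after the operation".

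The protocol gives no threshold for poor compliance and does not say who judges it.

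**The concern.** An exclusion that depends on how a patient handled the assigned postoperative regimen can be applied only once the arm is known. The regimens ask for opposite things. A nauseated or slow-to-recover patient might fail in a drinking arm and pass in group C, while a thirsty or hungry patient might do the reverse. There is no reason to expect the two sides to lose the same number or the same kind of patient.

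The primary endpoint is measured on day 1, after compliance has been observed. If those removed differ in insulin resistance from those kept, the retained groups can differ even when the drink does nothing. EOF 1 against EOF 2 is less exposed, because both arms face the same check and the same 30 ml step.

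The rule is also hard to apply consistently. A patient who takes 30 ml and then stops by choice has followed one sentence of 3.1.2 and may have breached another. Whether that patient is excluded is left to judgement.

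**Working it through.** The protocol states no exclusion rate, standard deviation or arm size, so there is no figure of its own to reproduce. The check has three steps.

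**1. Can these exclusions occur before allocation?** Bullets 3 and 4 refer to performing and accepting the intervention. Under 3.1.2 the interventions are postoperative and arm-specific, so compliance with them can be judged only after the arm is assigned. These are post-randomisation exclusions. No text says that failing the recovery check itself leads to exclusion, and that is not assumed here.

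**2. Is non-compliance defined in the drinking arms?** The two stated volumes agree only where 5 ml/kg × weight = 200 ml, that is, at 200 / 5 = 40 kg lean weight. At an assumed 55 kg, 5 × 55 = 275 ml, and 200 / 275 = 73%. Such a patient who drinks 200 ml has taken all of one stated amount and about three quarters of the other.

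**3. How large could the bias be?** This is an illustration on assumed inputs. Let pE and pC be the shares removed from a drinking arm and from group C. Let dE and dC be the mean of those removed minus the mean of those retained, in SD units. With no true effect, the retained mean of an arm lies p × d below its full mean, so:

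- shift (drinking arm minus group C) = pC·dC − pE·dE
- standard error = √[1/(n(1−pE)) + 1/(n(1−pC))]
- true two-sided error = P(|Z + shift/SE| > 1.96)

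First row in full, n = 50: shift = 0 − 0.20 × 0.5 = −0.10; SE = √(1/40 + 1/50) = 0.212; ratio = −0.471; error = P(Z > 1.489) + P(Z > 2.431) = 0.068 + 0.008 = 7.6%.

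| Removed, drinking arm | Removed, group C | dE, dC | Shift (SD) | Error, 50 per arm | Error, 100 per arm |
|---|---|---|---|---|---|
| 20% | 0% | +0.5, n/a | −0.10 | 7.6% | 10.2% |
| 20% | 10% | +0.5, +0.5 | −0.05 | 5.6% | 6.2% |
| 20% | 20% | +0.5, +0.5 | 0 | 5.0% | 5.0% |
| 5% | 20% | +0.5, +0.5 | +0.075 | 6.4% | 7.8% |
| 20% | 20% | +0.5, −0.5 | −0.20 | 14.5% | 24.4% |

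Simulated t tests (20,000 runs per case) agree in the four cases checked: 7.5% and 10.1% for the first row, 6.2% for the second at 100 per arm, and 8.0% for the fourth at 100 per arm.

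Equal removal rates protect only if the same kind of patient is lost on both sides. At 10% in each arm with differences of +0.5 and −0.5 SD, the shift is −0.05 − 0.05 = −0.10 SD.

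**The case against.** The strongest reply is that 4.3 does not say in words that these cases leave the analysis. The SAP is not shown and could keep every randomised patient. That is a fair limit, and the absence of an analysis set from the protocol is not the complaint. But the protocol does state an exclusion rule, and an SAP that analysed everyone would have to depart from 4.3 or explain how the two fit together.

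Other points stand in part.

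- Bullet 3 joins two conditions with an and, so poor compliance alone may not trigger it. Bullet 4 has no such double condition.
- The list is mixed, since another bullet covers unsigned consent. Some refusals might also fall under the separate dropout standard in 4.2, and the protocol does not say which rule takes precedence.
- Different tasks do not prove different failure rates, and the protocol has no compliance data. This is why only an unknown size and direction is claimed.
- Every input to the table is assumed. The largest errors need 20% loss on both sides with opposite differences, which nothing in the protocol suggests, and that case was not among those simulated. If the 0.5 SD were measured against the whole arm rather than against those retained, the first row would shift by 0.20 × 0.5 / 0.80 = 0.125 SD instead of 0.10.
- Symbols are visibly lost elsewhere in the text, so one may be missing before the 5 ml/kg figure. If it marked a limit, the gap between the volumes would narrow. The wording on drinking as needed and by wish would still leave non-compliance undefined, and the bias argument does not depend on the volumes.

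**Conclusion.** The concern holds. As written, 4.3 excludes patients after randomisation on behaviour that is defined differently in the drinking arms and in group C. Following it gives up the randomised comparison with group C, including the primary endpoint.

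The illustrated effect runs from nil to material, and its sign can reverse depending on which arm loses more patients and which kind. These sizes rest wholly on the assumed removal shares, the 0.5 SD difference and the assumed arm sizes. The conclusion that the comparison is open to bias rests only on the text of 4.3 and 3.1.2. This should be fixed, and wording can do most of it.

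**What to change.** 1. State that the primary analysis includes all randomised patients in the arm assigned, whatever they drank and whether or not the fast was kept.
2. Restrict bullets 3 and 4 of 4.3 to defining a per-protocol set for a sensitivity analysis.
3. Reconcile the passages in 3.1.2 on drink volume, drinking as needed and completion of the dose with each other and with 4.3. Then state for each arm, in advance, what counts as non-compliance. Which volume applies is for the investigators to settle.
4. Report the number of such cases and the reason for each, by arm.
5. As a separate clarification, state when randomisation takes place relative to the 3 h operation-time criterion in 4.2. That criterion applies to all three arms and is not claimed here as a source of selective loss.

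The cost is protocol wording and making sure that day-1 samples are taken from patients who did not comply. The estimated effect may be slightly diluted by patients who did not drink or who broke the fast.

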### 5 Informed consent

#### 5.1 The Informed Consent Form

The informed consent was in accordance with the ethical principles outlined in the Declaration of Helsinki. The informed consent form detailed the study protocol and process, and fully explained the risks of the study.

The informed consent form also states that the records of the individual identity must be kept confidential, but the research team and regulators can access the subject information.

#### 5.2 Informed consent process and record

Informed consent begins before the individual consent to participate in clinical studies and continued throughout the course of the clinical study.

#### 5.3 Confidential

Personal patient information will be given as confidential information. All patient data obtained from the patient cases will be kept as confidential. Patients will be identified by their name acronym and the numbers provided at the time of study inclusion. Patients or their families will be aware of the anonymity of the data and their right to protect their privacy. However, it is also important to understand the fact that the data will be submitted to the subject responsible unit or the government management authority, and may also be submitted to institutions such as the Ministry of Health for Protocol version: May 17, 2023

inspection and evaluation. The participating physician will keep a list of patient personal data (patient data and corresponding patient names) for confirmation of the record.

## 6. Quality control and quality assurance

### 6.1 Qualification of research unit and researcher qualification

The research unit shall have the experience in drug research, the facilities and conditions of the department where the project belongs shall meet the needs of safe and effective clinical research, and the researchers shall have the professional expertise, qualifications and ability to undertake the clinical research, and shall be trained in GCP regulations.

### 6.2 Training of the researchers

Before the start of the study, the research leaders of each center should organize the researchers to study the program, and only the researchers who have passed the program training can participate in the study to ensure that the researchers have a consistent understanding of the protocol. For important assessment scales, relevant personnel in the participating centers need systematic training and even obtain corresponding qualification certificates.

### 6.3 Surveillance of clinical trials

The hospital ethics committee and institutional review board may conduct a systematic review of the clinical trial-related activities and documents, to evaluate whether the trial was conducted in accordance with the test protocol, SOP, and relevant regulations, and whether the test data are timely, true, accurate, and complete records. The audit should be performed by those who do not directly involve the clinical trial.

## 7. Organization and management of the research

### 7.1 Change of the scheme

All additional or referenced appendices are integral parts of the scheme. No one shall make any modifications or revisions to any part of the research protocol, as signed by the investigator and the principal of the project, unless these changes or revisions have been fully discussed. And through the unanimous consent of the researcher and the Protocol version: May 17, 2023

subject leader.

Any agreed modifications will be recorded and will be signed by the investigator and the project leader and filed with the protocol.

## 7.2 Retention of the records

The investigator shall keep all the detailed original documents of the subject and record the trial process, medication status, laboratory examination data, safety data and efficacy assessment in the case report form. The recorded data shall be complete, timely and clear. The original documents and medical records should be clear, detailed and easily identified by those participating in this clinical trial.

The case report form and the original files can only be modified by the investigator. No modification to the case report form and the original file shall smear the original data off. The correct way to modify is to line the original data, and then write the modified data next to the original data, and sign the date and the name of the modification.

Test data shall be retained until 5 years after the termination of the test.

## 7.3 Early termination of the study

The leader of the project decides to stop or interrupt the study in advance in the case of force majeure, and should inform the doctors involved in the study in writing. Similarly, any participating unit that decides to withdraw from the study for any reason should also notify the project leader in written form.

## 7.4 Research, supervision and inspection

### 7.4.1 Research supervision

Inspectors must follow the drug clinical trial quality management specification (GCP) and standard operation procedures (SOP), visit the research unit regularly or according to the actual situation, supervise the clinical trial work and progress, check, confirm all data records and reports, correct and complete, consistent with the original data, ensure the clinical trial in accordance with the clinical trial protocol, the researchers should actively cooperate with the inspectors. The specific contents of the inspector include:

a) Ensure that the test undertaking unit has appropriate conditions, including staffing

Protocol version: May 17, 2023

and training, complete laboratory equipment, good operation, various inspection conditions related to the test, an estimated sufficient number of subjects, and the participants to be familiar with the requirements in the test plan;

- b) Monitor the implementation of the trial program during the trial, confirm that the informed consent of all subjects is obtained before the trial, understand the enrollment rate of the subjects and the progress of the trial, and confirm that the selected subjects are qualified;
- c) Confirm that the records and reports of all data are correct and complete, and that all case report forms are entered correctly and consistent with the original data. All errors or omissions have been corrected or indicated, signed and dated by the Investigator.
- d) Verify that all adverse events are recorded, and that serious adverse events shall be reported and recorded within the specified time;
- e) Clearly and truthfully record the failed visits, unconducted tests, and undone checks should be made, and whether the errors and omissions should be corrected;
- f) The written inspection report shall be completed after each visit, which shall state the date, time, name of the inspector, the findings of the inspection, etc.

#### 7.4.2 On-site inspection

The responsible unit may conduct an on-site inspection of the research at a clinical research institution. The audit includes the required test documents, records of the informed consent process, and the consistency of the eCRF and the original documents. But also the content and scope of the inspection can be increased according to the situation. The investigator agrees to participate at a reasonable time and in a reasonable manner.

### 8. Investigators' responsibilities

#### 8.1 Participation of doctor responsibilities

The participating physicians will conduct the study following the study protocol and confirm the accuracy of the data entered. The participating physicians should be responsible for obtaining written signed informed consent for data collection from the study subjects.

## 8.2 Responsibility of the project leader

The project leader takes all reasonable steps and provides sufficient resources to ensure the implementation of the research, mainly involving the following aspects:

- a) Ensure that the study complies with relevant national and local regulations, including ethical requirements, patient data protection regulations, etc.
- b) Ensure the effectiveness of quality control and analysis of research results.

## 9. Share results

The intellectual property rights, trial data and research results related to this study are jointly owned by Nanjing First Hospital and the Department of Anesthesiology.

The intellectual property rights, trial data and research results related to this clinical study are owned by Nanjing First Hospital and the Anesthesiology Department.

## 10. Ethics principles and requirements for clinical research

Clinical research will follow the world medical congress "declaration of Helsinki" and the national health and family planning commission of the People's Republic of China "involving people biomedical research ethics review method" and other relevant provisions, the specific implementation of informed consent, the privacy protection, research free and compensation, risk control, special subject protection and research related damage compensation principles and requirements. The clinical study was performed before the ethics committee approved the trial protocol. Before each subject is enrolled in the study, the investigator has the responsibility to present the subject or / and his legal agent about the purpose, procedures of the study and possible risks, and sign a written informed consent form that their participation in the clinical study is completely voluntary, that they may refuse to participate or withdraw from the study at any time at any stage of the trial without discrimination and retaliation, and their medical treatment and interests are not affected. The informed consent form should be retained as a clinical research document for future reference to effectively protect the subjects' personal privacy and data confidentiality.
